9.2.9. Clinical Activity Assessments

All clinical activity assessments and imaging in the prospective cohort will follow the standard of care (AASLD¹⁰ and/or EASL¹¹ HCC Guidelines) and imaging will be performed as described in Table 2. These guidelines recommend dynamic computed tomography (CT) or magnetic resonance imaging (MRI) to assess response approximately one month after HCC treatment interventions (resection, loco-regional, or systemic therapies), every 3 months for the first year after HCC treatment intervention(s), and every 6 months thereafter to complete up to 24 months.

All clinical data and imaging records, including raw images, will be collected and analyzed, as appropriate, during the study.

9.3. Variables

The prospective DAA-PASS cohort will include information on participant demographics, laboratory values, medical history events, concomitant medication use (including hepatotoxic medications), alcohol use, staging of liver disease and HCC (including but not limited to Child-Pugh score, Model for End Stage Liver Disease [MELD] score, performance status, and BCLC stage), HCC treatment intervention(s) and response, tumor assessments, additional liver imaging information, prior and subsequent HCV treatment (including IFN), DAA therapy, and virologic response data.

The data for the prospective DAA-PASS cohort include imaging collection and details of DAA therapy from the TARGET-HCC database. The database includes information on participant demographics, laboratory values, comorbid liver conditions (including but not limited to HCV status), medical history events (including adverse events), concomitant medication use, HCV treatment history, HCC staging information, tumor assessment and response, HCC treatment history, and additional liver imaging information.

The model will include the following baseline covariates as available: alpha-fetoprotein (AFP) level, albumin level, platelet count, MELD score, age in years, gender, diabetes status, alcohol use/AUDIT score ≥ 7 , HCC treatment modality, and study centre (see Section 9.7.6.2).

The historical cohort will include similar data extracted from the ITA.LI.CA database (where available). Information related to the variables collected in the historical cohort is described in Section 9.7.9.

Definition of HCC Recurrence

The objectives are based on the analysis of early HCC recurrence (see Section 9.1.1) as indicated on imaging following Enrollment/Baseline (date of first HCC-free image; see Section 9.1.1). Periodic screening for HCC recurrence will rely on conventional imaging-based evaluations. HCC recurrence is defined (see Section 9.1.1) as having evidence of enhancing lesions suggestive of new HCC on imaging after successful treatment of HCC. The onset of HCC recurrence will be assumed to occur during the time interval between a previous negative imaging evaluation and the subsequent positive imaging evaluation. The time of onset will thus be interval-censored instead of being known precisely. Participants will be considered to have an event if they have an HCC recurrence in an interval as demonstrated by imaging.

DAA exposure

The analyses for the Primary Objective and Secondary Objective B estimate the risk of HCC recurrence associated with exposure to DAA therapy for HCV versus no DAA therapy using a proportional hazards model with DAA therapy included as a time-varying exposure variable. DAA therapy can be initiated at any time after Enrollment/Baseline when absence of detectable HCC is documented (i.e., successful treatment of HCC). For purposes of fitting the statistical model, the time-dependent risk associated with DAA therapy will be assumed to start at the time of the image preceding the start of DAA therapy and is a positive risk in all subsequent intervals. For purposes of these analyses, it will be assumed that the risk of HCC recurrence is a function of DAA exposure only and does not require participants to complete the prescribed HCV regimen or achieve sustained virologic response (SVR). Sensitivity analyses will be used to explore the impact on the estimate of the HR associated with DAA exposure relative to no DAA therapy related to the date of DAA therapy initiation.

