9. RESEARCH METHODS

9.1. Study Design

9.1.1. Overall Design

This prospective, observational study will estimate the risk of early HCC recurrence associated with DAA therapy exposure relative to no DAA therapy exposure during routine clinical care of HCV-infected patients with previous successfully treated HCC using a prospective cohort from TARGET-HCC.

DAA-PASS will include a prospective cohort and data from a historical cohort.

For the purposes of data analysis in DAA-PASS, the following definitions will be used:

- **Enrollment/Baseline:** the date of the **first HCC-free** (radiological) **image**
- **Successful treatment of HCC:** no evidence of enhancing liver lesions and no extrahepatic lesions consistent with new or persistent HCC on radiological imaging (see Section 9.2.9) after HCC treatment intervention
- **First HCC-free image (Index Date):** the first radiological image (see Section 9.2.9) that showed confirmation of **successful treatment of HCC**
- **Follow-up:** from Enrollment/Baseline up to 24 months
- **HCC recurrence:** evidence of enhancing liver lesions or extrahepatic lesions consistent with recurrence or new HCC on radiological imaging (see Section 9.2.9) after **successful treatment of HCC**
- **Early HCC recurrence:** **HCC recurrence** within the follow up period after **the first HCC-free image**

Prospective Cohort Design

[figure not shown]
The prospective DAA-PASS cohort will include the following periods:

- Screening (participants identified in TARGET-HCC who fulfil the screening criteria [see Section 9.2.2])
- Enrollment/Baseline (participants with their first HCC-free image who fulfil the enrollment criteria [see Section 9.2.3])
- Follow-up (up to 24 months from Enrollment)

During the follow-up period, participants will be managed per local standard of care which includes follow-up imaging according to guidelines established by the American Association for the Study of Liver Disease (AASLD) and the European Association for the Study of the Liver (EASL): AASLD Guidelines for the Treatment of Hepatocellular Carcinoma¹⁰ and EASL–European Organization for the Research and Treatment of Cancer (EORTC) Clinical Practice Guidelines: Management of Hepatocellular Carcinoma¹¹ (see Section 9.2.9).

Upon completion of or early discontinuation from DAA-PASS, participants will continue to be followed in TARGET-HCC (see Section 9.2.6).

Figure 1. Prospective DAA-PASS Cohort Schema

[figure not shown]
Historical Cohort Design

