9.2.2.1. Screening Inclusion Criteria

Participants must meet all of the following to be eligible for participation in DAA-PASS:

Current participant in TARGET-HCC

Adults, age ≥ 18 years

First diagnosis of HCC (mixed HCC/cholangiocarcinoma may be included). Diagnosis may be histological/cytological and/or radiological.

BCLC Stage A

Underwent, undergoing, or planned to undergo therapy for HCC, with exception that transplant as prior or planned treatment for HCC is excluded.

HCV RNA positive

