9.2.6. Completion and Discontinuation of Participants

A participant will be considered as complete in the DAA-PASS, if they meet any of the following:

- Complete up to 24 months of Follow-up after Enrollment/Baseline
- Death (due to any cause) during Follow-up while still enrolled in DAA-PASS

Participants will be discontinued from DAA-PASS for the following reasons:

- Participant choice, withdrawal of consent
- Lost to follow-up
- Administrative (e.g., site closure, Sponsor termination of the study, study completion as defined in Section 9.2.7)

Although participation in DAA-PASS for each participant will end after Screen Failure (at Screening or Enrollment/Baseline), Completion, or Premature Discontinuation, living participants will remain enrolled in TARGET-HCC. For clarity, any subsequent data collected after participation in DAA-PASS will only be available as part of TARGET-HCC.

If a participant chooses to withdraw from TARGET-HCC, they will consequently also be choosing to withdraw from DAA-PASS.

If a participant chooses to withdraw from DAA-PASS, all data collected up to the point of withdrawal will remain for use in the study database, unless otherwise prohibited by local regulations, but no further data may be collected. A request to withdraw must be documented in the participant's medical record by the study site personnel to be consistent with privacy guidelines and regulations.

For participants who die during their participation in DAA-PASS, it will be the responsibility of the Investigator to assign a cause of death based upon available clinical information, hospital records, and/or death certificate; the relevant death information will be included in the database. Site staff may also search publicly available sources for any information regarding death of a participant and may submit that information for entry into the database after the discontinuation date.

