9.7.3. DAA Exposure as Time-Varying Exposure

Individual participants in the prospective DAA-PASS cohort can contribute person-time to both DAA exposure and no DAA exposure. DAA exposure is a function of time. The no DAA exposure starts at the enrollment/baseline image (Index Date; i.e., successful treatment of HCC) and continues until the participant has an event (i.e., HCC recurrence), initiates DAA therapy, completes the study without initiating DAA therapy, or is otherwise censored. The DAA exposure starts at the first date a DAA is initiated and continues until the participant has an event, completes the study, or is otherwise censored. Participants are censored in whichever exposure type they are in (no DAA exposure or DAA exposure) if they receive IFN treatment, a liver transplant, die, withdraw from the study, or are otherwise removed or lost to follow-up while enrolled in DAA-PASS. Participants that receive DAA therapy starting on the date of Enrollment/Baseline only contribute person-time to DAA exposure and participants that never receive DAA therapy only contribute person-time to the no DAA therapy exposure person-time. The completion of the study is defined by obtaining imaging corresponding to the 24-month follow-up assessment. Note that participants who received a liver transplant while enrolled in DAA-PASS will continue to be followed up to 24 months from Enrollment/Baseline.

Additional information on DAA therapy will be collected including, as available, the DAA prescribed, duration of dosing and planned duration, and SVR response. These will be summarized descriptively.

9.7.4. Coding Convention for HCC Recurrence and DAA as Time-Varying Exposure for the Primary Analysis

This section provides additional details on the coding of the HCC recurrence endpoint for analysis. The primary model of time of onset is based on interval-censoring as outlined in Section 9.7.6.1. The intervals between imaging evaluations are not required to have a fixed length and a participant with a missed visit would simply experience an extended interval -- assuming they have a later follow-up assessment. For the analysis, individuals will have a record of an event or not corresponding to each available interval of no DAA exposure or DAA exposure. The table below provides some examples of participant data where t_{i0} is baseline and t_{ij} for $j = 1$ to n_i represent sequential imaging assessment times for the i^{th} participant:

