9.7.5. Conventions for Missing Data and Post-Baseline Data Collection

DAA-PASS collects select covariates at the time of screening. Additional data will be collected as it is available within the participant’s record. DAA-PASS has no data collection requirements that are not considered standard of care. Outside of imaging for the assessment of HCC recurrence, data will be available when they appear in the participant’s medical record and are not otherwise considered missing. Details will be provided in the SAP as appropriate.

The analysis of the interval-censored data accommodates missed or unavailable HCC assessments for a given time interval if a later HCC assessment is completed. However, the statistical analyses will include a participant’s data only up to the time of their last completed HCC assessment and will be censored after that time.

9.7.6. Analysis of Early Risk of HCC Recurrence Associated with DAA Therapy (Primary Objectives and Secondary Objective B)

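### A death from HCC with no positive image after baseline is censored as recurrence-free at the last negative image, and no listed sensitivity analysis addresses this

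*Protocol*

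**What the plan says.** Protocol section 9.1.1 defines recurrence as "evidence of enhancing liver lesions or extrahepatic lesions consistent with recurrence or new HCC on radiological imaging". Section 9.3 repeats that an event needs imaging proof ("Participants will be considered to have an event if they have an HCC recurrence in an interval as demonstrated by imaging") and places onset "during the time interval between a previous negative imaging evaluation and the subsequent positive imaging evaluation". No other right-hand end of the interval is provided.

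Section 9.7.3 censors participants in their current exposure state "if they receive IFN treatment, a liver transplant, die, withdraw from the study, or are otherwise removed or lost to follow-up while enrolled in DAA-PASS". It makes no exception for death from HCC. The last row of Table 3 ends a censored participant's intervals at the last imaging evaluation, and section 9.7.5 agrees: "the statistical analyses will include a participant’s data only up to the time of their last completed HCC assessment".

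The protocol does collect cause of death. In section 9.2.6, "it will be the responsibility of the Investigator to assign a cause of death based upon available clinical information". For the first tumour, section 9.2.2.1 accepts tissue as well as imaging ("Diagnosis may be histological/cytological and/or radiological"); the recurrence definition has no counterpart.

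**The concern.** Enrolment requires an HCC-free image (section 9.2.3.1), so a death correctly attributed to HCC means that the tumour returned or was never cleared. Either way, treating the participant as recurrence-free up to the last negative image and uninformatively censored afterwards is wrong for that person. This differs from the usual competing-risk question about deaths without recurrence. Here the participant leaves the risk set because of the outcome, while the proportional hazards model assumes that censoring carries no information about it.

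The stake is the primary hazard ratio of a safety study that now expects only 40 to 70 participants. Safety reporting does not pick these deaths up either: section 11.3 excludes death from HCC from serious adverse events. They would appear only in the optional descriptive summary of survival and deaths in section 9.7.7.

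**Working it through.** **1. Following one participant through the rules.** Take a negative image at month 12, no further image, and death from HCC at month 16.

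- Sections 9.1.1 and 9.3: no positive image, so no event.
- Section 9.7.3: death is a censoring reason.
- Table 3 and section 9.7.5: data end at month 12.
- Result: recurrence-free to month 12, then censored.

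**2. Looking for a remedy elsewhere in the protocol.** The sensitivity analyses listed in section 9.7.6.3 cover DAA started in the recurrence interval, follow-up censored for interferon, time-dependent AFP and MELD, and extra covariates. The weights in section 9.7.8 model only censoring caused by the start of DAA. Section 9.9.1 concedes that non-ignorable censoring could bias results, mainly through transplant, but ties no particular analysis to it.

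**3. Expected events.** The protocol gives event counts only for the former size of 600: 122 at 15% per year and 195 at 25% per year (section 9.5.1). Without censoring, 600 × (1 − 0.85²) = 166.5 and 600 × (1 − 0.75²) = 262.5. The stated counts therefore include censoring at a rate the protocol does not give. With recurrence hazard h = −ln(1 − r) and an independent censoring hazard c,

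events = N × h/(h + c) × [1 − exp(−2(h + c))].

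Solving for c gives 0.35 per year in both scenarios:

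- r = 15%, h = 0.1625: 600 × 0.3171 × 0.6412 = 122.0
- r = 25%, h = 0.2877: 600 × 0.4511 × 0.7207 = 195.1

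Both stated counts are reproduced, so c = 0.35 is a reasonable working assumption.

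For the current plan at 35% per year, h = −ln(0.65) = 0.431 and the event share is 0.431/0.781 × [1 − exp(−1.562)] = 0.436. That gives 0.436 × 40 ≈ 17 events and 0.436 × 70 ≈ 31 events.

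**4. Weight of one case.** 1/17 ≈ 6% and 1/31 ≈ 3% of all events. Three cases would be about 10% to 18%. These figures assume 24 months of follow-up for all; the June 2021 cut-off in section 4.4 shortens it for late entrants, which lowers the event count and raises each share somewhat.

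**5. Effect on the hazard ratio.** If shares m1 (on DAA) and m0 (off DAA) of true recurrences are never imaged, the observed HR is roughly the true HR × (1 − m1)/(1 − m0). For a true HR of 1.0, with assumed shares:

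| m1 (DAA) | m0 (no DAA) | Observed HR |
|---|---|---|
| 10% | 10% | 1.00 |
| 15% | 5% | 0.89 |
| 20% | 5% | 0.84 |
| 5% | 15% | 1.12 |

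Equal loss leaves the HR about where it was and costs precision. Unequal loss moves it either way.

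**The case against.** The strongest reply is that the sequence must be rare. Section 9.4 abstracts imaging from local radiology reports throughout follow-up, and section 9.7.4 does not require intervals of fixed length. Any scan taken as the patient deteriorates would make the participant an event. Only a death with no positive scan at all is lost. That stands, and it limits the number of cases.

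A second reply is that imaging-defined recurrence is objective and prespecified. Cause of death is assigned from clinical information, hospital records or a death certificate, by an investigator who knows DAA status, in patients who all carry an HCC diagnosis. That also stands. It argues against moving such deaths into the primary endpoint, but not against a sensitivity analysis.

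A third reply is that section 9.9.1 promises sensitivity analyses, the list in 9.7.6.3 is open-ended, and an analysis plan may add more. But the event and censoring rules are fixed in the protocol, and no analysis there is aimed at this consequence.

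A reader might go further in three ways that the documents do not support.

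- *That the rule biases the HR towards no harm.* This needs more loss on DAA than off it, and nothing in the protocol shows that. The wider six-month imaging gaps in year 2, when most participants are expected to be on DAA, do not establish it: the model compares exposure states at the same follow-up time, so a loss that depends on time alone does not favour either state.
- *That biopsy-proven recurrence is censored outright.* Biopsy is not a censoring reason, and a later positive image would still count. The loss arises only if no positive image follows.
- *That tumour found in an explant should count as an event.* Explant pathology exists only for transplanted participants, and section 9.7.6.1 links DAA use to transplant access and HCV status. Counting it would add a detection route tied to exposure. The protocol never mentions explant findings.

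**Conclusion.** The point holds in a limited form. By the protocol's own rules, a death from HCC without a positive image is coded as a non-event at the last negative image. The censoring is caused by the outcome, and no listed analysis examines it.

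The number of such cases is unknown and probably small. Each is about 3% to 6% of an expected 17 to 31 events, given 35% recurrence per year, 24 months of follow-up and the back-solved censoring hazard of 0.35 per year. The hazard ratios of 0.84 to 1.12 shown above are illustrations under assumed losses, not estimates. They are modest beside the planned confidence limits of 0.46 to 2.82 at 70 participants (section 9.5.1). That supports adding a sensitivity analysis. It does not support replacing the primary definition.

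**What to change.** Keep the imaging-based definition as primary. Add to section 9.7.6.3, as a firm commitment rather than an option, a sensitivity analysis in the prospective cohort that also counts as events:

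- (a) death with HCC as the investigator-assigned cause and no earlier positive image, with onset between the last negative image and death;
- (b) biopsy-proven recurrence without a positive image, with onset between the last negative image and the specimen date.

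Label the exposure of these intervals by the Table 3 convention and leave the other censoring rules unchanged. Report the number of such cases by DAA exposure state. Report HCC found in explants descriptively only. Extend the analysis to Secondary Objective B only if the historical database holds cause of death; the variables listed in section 9.7.9 do not include it. Otherwise, extra events would be counted only in the cohort that supplies all the exposed time.

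The interval-censored model already takes intervals of any length, so no new method is needed. Cause of death is already recorded. Biopsy results after baseline should be available through the general collection of prospective medical-record data (note to Table 2). The cost is a little programming and reporting, and a few events that depend on clinical attribution by an investigator aware of DAA status. Setting this analysis beside the primary result shows how much those events matter.

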Table 3. Handling of HCC Recurrence and DAA as Time-Varying Exposure

Situation	Handling in Model
Participant completes study without DAA therapy and without detection of a recurrence event	Participant has n imaging evaluations that define n intervals $(t_{i0}, t_{i1}]$, ..., $(t_{i(n-1)}, t_{in}]$ which are labeled to indicate no events and no exposures have occurred.
Participant receives DAA in an interval and has no events	Participant does not experience recurrence during the study and first receives DAA during $(t_{i(m-1)}, t_{im}]$ with $m \leq n_i$. This and subsequent intervals are labeled as being exposed to DAA initiation. If a participant receives DAA in the first interval, they are included as having DAA therapy from the beginning of follow-up.
Participant has an HCC recurrence detected at time t_{ik} .	Participant experiences a recurrence during $(t_{i(k-1)}, t_{ik})$. For this participant $n_i = k$. Some of the k intervals may be labeled as having no DAA therapy, and some as having DAA exposure.
Participant discontinues prematurely or is censored	Participant has multiple intervals up to the last imaging evaluation at time t_{ik} with $n_i = k$.

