9.7.6.3. Supporting Summaries (Primary Objective)

The following activities are planned to evaluate the robustness of the analysis results to perturbations of the methods and assumptions used, and to fully explore and describe the data.

- Evaluate time to HCC recurrence by treatment of initial HCC.
- Utilize goodness-of-fit measures to explore the appropriateness of the model.
- Evaluate homogeneity of the DAA response across study sites. This may involve only larger sites, pooling, or considering regional differences.
- Descriptive statistics will be used to explore the impact of the period of time the DAA therapy was initiated. A proportional hazards model will also be used to separately code the DAA treatment effect based on those who initiate therapy up to 6 months and after 6 months from the baseline in order to explore the impact of the timing of the initiation of DAA therapy.

- Sensitivity analyses may include: analyses to understand the impact of the proposed handling of DAA therapy that initiates in the interval where a HCC recurrence occurs, an analysis that adds back in the participant follow-up time for those censored due to IFN use, an analysis using time-dependent values of AFP and the MELD score, and an exploration of additional covariates in the model.

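### The primary coding backdates DAA exposure to the image before DAA start, which contradicts section 9.7.3 and attenuates a true excess risk

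*Protocol*

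**What the plan says.** Two rules for the start of exposed time stand side by side in the protocol.

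- **Backdated rule.** Section 9.3 (DAA exposure), which covers the Primary Objective and Secondary Objective B, says that for model fitting the DAA risk "will be assumed to start at the time of the image preceding the start of DAA therapy". Table 3 in section 9.7.4, whose heading names it as the coding for the primary analysis, says of the interval in which DAA is first received: "This and subsequent intervals are labeled as being exposed to DAA initiation". It adds: "If a participant receives DAA in the first interval, they are included as having DAA therapy from the beginning of follow-up".
- **Start-date rule.** Section 9.7.3 says: "The DAA exposure starts at the first date a DAA is initiated and continues until the participant has an event". Unexposed time runs until DAA is initiated, and the group with exposed time only is narrow: "Participants that receive DAA therapy starting on the date of Enrollment/Baseline only contribute person-time to DAA exposure". Sections 9.1.1 and 9.7.9 likewise place the time before DAA in the unexposed condition.

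On safeguards, section 9.3 commits to sensitivity analyses concerning the date of DAA initiation, without giving a method. Section 9.7.6.3 lists a narrower, optional one: "Sensitivity analyses may include: analyses to understand the impact of the proposed handling of DAA therapy", limited to starts in the interval where a recurrence occurs.

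**The concern.** The rules disagree for every participant who starts DAA between two images. A participant who starts in month 2 has about two months of unexposed time under section 9.7.3 and none under Table 3. With 90% of recurrence-free participants assumed to be treated by 24 months (section 9.5.1), this touches most of the cohort.

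The coded rule is not neutral. Time before the first dose carries the unexposed hazard, yet it enters the exposed group together with any recurrence arising in it. Mixing lower-hazard time into the exposed group lowers the estimated hazard ratio when DAA is harmful. In a safety study requested to look for excess recurrence, an avoidable error in that direction should not sit in the primary estimate.

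**Working it through.** **Inputs from the protocol**

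- Images at 3, 6, 9, 12, 18 and 24 months (9.2.4).
- DAA uptake of 42% by 6 months, a further 44% by 12 months and 4% between 12 and 24 months (9.5.1).
- Recurrence of 15%, 25% or 35% per year, and N=70 at 35% (9.5.1).

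**Assumptions, because the protocol gives no figure**

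- Constant hazards and exponential censoring.
- DAA starts uniform within each uptake window.

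**Step 1: reproduce the protocol's event counts to fix the censoring rate.** Events = 600 × λ/(λ+c) × [1 − exp(−2(λ+c))], with λ = −ln(1 − annual rate).

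- At 15%, λ = 0.1625. Solving for 122 events gives c = 0.35 per year, since 600 × 0.3171 × 0.6412 = 122.0.
- At 25%, λ = 0.2877. The same c gives 600 × 0.4511 × 0.7207 = 195.1, against the stated 195.
- c = 0.35 means 1 − exp(−0.35) = 29.5% censored per year. Without censoring the counts would be 166.5 and 262.5.

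**Step 2: the mechanism.** A start at a uniform point in a 3-month interval moves 1.5 months of unexposed time into exposed time on average; in a 6-month interval it moves 3 months. For a true hazard ratio of 2.0, the average relative hazard over such an interval is about (1 + 2)/2 = 1.5, but the coding treats it as fully exposed.

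**Step 3: size.** An interval-censored proportional hazards likelihood was fitted to large simulated cohorts (400,000 participants per setting, repeated at 1,500,000), once with each coding. Results at 35% per year, DAA start independent of undetected recurrence:

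| True HR | Whole-interval coding (9.3, Table 3) | Start-date coding (9.7.3) |
|---|---|---|
| 1.0 | 1.00–1.01 | 1.00–1.01 |
| 1.5 | 1.36–1.38 | 1.49–1.51 |
| 2.0 | 1.73 | 1.99 |
| 3.0 | 2.42–2.43 | 3.00–3.01 |

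At 2.0 the loss on the log scale is 1 − ln 1.73/ln 2 = 1 − 0.548/0.693 = 21%. Across 15% to 35% per year, whole-interval coding gives 1.36–1.40, 1.73–1.76 and 2.42–2.50 for true values of 1.5, 2.0 and 3.0.

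**Step 4: an extreme alternative.** Suppose DAA is never started once an undetected recurrence has begun, so that the backdated time is event-free. At 35% per year:

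| True HR | Whole-interval coding | Start-date coding |
|---|---|---|
| 1.0 | 0.64–0.65 | 0.84–0.85 |
| 1.5 | 0.93–0.94 | 1.24–1.26 |
| 2.0 | 1.22–1.23 | 1.66 |
| 3.0 | 1.79–1.80 | 2.49–2.50 |

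Both codings are then biased, start-date coding less so.

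**Step 5: precision at N=70, 35% per year, HR 1.0.** The stated bounds of 0.46 to 2.82 imply SE = ln(2.82/0.46)/(2 × 1.96) = 1.813/3.92 = 0.463. The simulated design gives 0.461 with whole-interval coding and 0.516 with start-date coding. Centred on 1, exp(±1.96 × SE) is 0.41–2.47 and 0.36–2.75. The information lost is 1 − (0.461/0.516)² = 20%.

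**The case against.** Several points on the other side stand.

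- **There is an operational rule.** A reader might infer that the primary analysis is undefined. Section 9.3 states its rule for model fitting and section 9.7.4 is headed as the primary coding, and the two agree. It is a disclosed convention for interval-censored onset. The fault is that section 9.7.3 was not reconciled with it.
- **There is a committed safeguard.** A reader might infer that the optional analysis in section 9.7.6.3 is the only one. Section 9.3 commits to sensitivity analyses on the DAA start date, and section 9.9.1 commits to robustness analyses generally. Their detail may properly sit in the statistical analysis plan.
- **The direction is conditional.** A reader might infer that the null is always unbiased and that a harmful hazard ratio is only ever drawn toward 1. Step 4 shows otherwise: a true 1.5 can fall below 1, and start-date coding does not guarantee an unbiased result either. In the other direction, the bias shrinks if an image happens to be taken just before DAA start.
- **The shift is small against sampling error.** From 2.0 to 1.73 is 0.145 on the log scale, about 0.3 of one standard error at N=70 (0.145/0.463). The 6-month intervals concern only the 4% assumed to start after month 12.
- **The fix is not free.** A reader might expect a negligible loss of precision. Step 5 shows about 20% of the information.

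What does not stand is that interval censoring requires backdating. Recurrence onset is interval-censored; DAA start is a date, on which section 9.7.3 itself relies. A sensitivity analysis also leaves the attenuated figure as the primary result.

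**Conclusion.** The point holds. The protocol defines the start of DAA exposure in two incompatible ways, and the one set for the primary model understates a real excess risk. Under the base assumptions (about 30% censoring per year, starts uniform within windows and independent of undetected recurrence, constant hazard ratio) true values of 1.5, 2.0 and 3.0 are estimated as about 1.37, 1.73 and 2.4, with no bias at 1.0. The bias grows with missed scans, because section 9.7.4 lets the interval lengthen, and grows further if DAA is withheld when recurrence is emerging.

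The agreement between the stated precision at N=70 and whole-interval coding (0.463 against 0.461) might suggest that the sponsor computed its bounds that way. The protocol does not say so, and the stated interval is centred on √(0.46 × 2.82) = 1.14, so this should not be inferred. What follows is narrower: the claim to distinguish from a hazard ratio of 3.0 at N=70 has not been shown to hold under start-date coding. With SE 0.516 the upper bound is 2.75 if centred on 1, and 1.14 × 2.75 = 3.13 if centred where the stated interval is.

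**What to change.** - Use one definition in sections 9.3 and 9.7.3 and in Table 3: exposure begins on the recorded DAA start date. Remove the sentence in section 9.3 that starts the risk at the preceding image. In Table 3, amend the row for a DAA start without an event, and state in the recurrence row how the start interval is handled.
- In the interval-censored likelihood, split the cumulative hazard at the start date D. For an image at time R after D, H(R) = H₀(D) + HR × [H₀(R) − H₀(D)]. A recurrence between images at L and R contributes S(L) − S(R). The baseline hazard must be specified within intervals, for example as piecewise constant.
- Keep whole-interval coding as a committed sensitivity analysis, and report the two estimates together.
- Recalculate the precision figures in sections 4.8, 9.5.1 and 9.7.9 under the adopted rule, including the statement about a hazard ratio of 3.0 at N=70.
- State as a limitation that start-date coding is also biased if DAA initiation depends on emerging recurrence.

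The cost is wording, programming and the recalculation, plus a wider interval (standard error about 0.52 instead of 0.46 at N=70). DAA therapy details are already recorded, so no new data are needed.
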